Monitoring Postoperative Recovery from Cancer Surgery is Challenging after Discharge. Due to changes in healthcare and advances in surgical techniques, surgeons are asked to discharge patients earlier after surgery. Operations that were previously associated with 10-20 day hospital stays are now outpatient or short-stay procedures. Postoperative complications that traditionally arise in the hospital are also developing in the community and at home. The current delivery model for post-discharge care is largely inefficient and not proactive.³² Home health nurses are often dispatched for unresolved acute problems. Patients may contact the hospital when acute problems arise, but are often unaware of when to contact their surgeons (RQ-3). This often requires hours or days to resolve, and is burdensome for patients, families, and the healthcare system. Delays in communicating critical conditions may escalate problems beyond outpatient care. In critical situations, emergency room visits within the same healthcare system or at a different institution occur, resulting in inefficient and fragmented care.

The burden of postoperative hospital readmissions after major cancer surgery is high.³³⁻³⁵ Depending on the tumor site, 90-day readmission rates for major cancer surgery range from 23-43%.³⁶ Published data suggest that 30- and 90-day readmission rates are 30% and 43% for cystectomy, and 22% and 35% for esophagectomy and pancreatectomy.^{36, 37} Hospital readmissions are burdensome, and result in higher 1-year mortality rates, and delays in timing and eligibility for adjuvant therapies.³³ Predictors of readmissions are similar across different tumor sites, and include functional impairments, comorbid conditions, and postoperative complications.^{36, 38}

There are Critical Knowledge Gaps on the Impact of Patient-Centered Outcomes in Cancer Surgery. The impact of routine symptom monitoring is predominantly tested in chemotherapy settings.^{39,40} These findings suggest a positive effect on patient-provider communication⁴¹⁻⁴⁴, detection of unrecognized problems^{40, 44-47}, guiding clinical care^{46, 48-50}, health outcomes⁵⁰⁻⁵⁴, and survival.⁹ Few studies are conducted in surgical oncology, and few

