4.4 Randomization and/or Dose Level Assignment

Each patient will be randomly assigned to either the remote perioperative telemonitoring or surgeon only perioperative care arm, using a stratified and blocked randomization. Strata will be defined by diagnosis (GI, GU, GYN) and surgical technique (minimally-invasive versus open). Variable block sizes will be used to maintain approximate balance and pre-assignment masking.

[figure not shown]

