13.2 Statistical Analysis Plan

Data Management - We expect a total of 12 symptom evaluations per participant over the 3-4 month study duration. With a total sample of 332, this yields approximately 4,000 data collection encounters overall. We expect a large number of daily steps data observations per subject, as functional recovery data will be continuously recorded on a daily basis over the study duration.

Data will be transferred in real-time (within 2 minutes of participant completion) from TapCloud™ to a REDCap (Research Electronic Data Capture) study database. Daily step count will be continuously transferred to the study database in real-time. The database resides in secure COH research networks for research team access only. An assigned master's-level Statistical Research Associate (SRA) with paid effort on the project will be responsible for coordinating monthly data transfer, auditing, and data cleaning. In the process of data transfer and mergers, the study biostatistician ([name]), SRA, and TapCloud™ representative will audit and clean the data, apply formats in statistical software, and export data into REDCap database.

Handling Missing Data and Lost to Follow-Up - We will integrate the following strategies to prevent, detect, and remedy missing data in real time. First, participants will receive a total remuneration of \$50 for providing data. Second, research staff will provide telephone/email reminders before each of the scheduled data collection timepoints to maximize adherence. Regular contact will also be provided to remind participants to wear the accelerometer. Third, research staff will provide each participant with a simple study calendar with data collection dates. Fourth, if no data is completed by participants, research staff will contact the participant in real-time to engage and assess. The Statistical Methods section below describes how data missing not at random will be handled in the analyses.

Preliminary Analysis - Descriptive statistics will be used to summarize all variables. Characteristics of participants at baseline will be reported in tabular form using appropriate descriptive statistics. Prior to hypothesis testing, the relationship between demographic variables and primary outcome variables (daily step count, postop complications) will be examined. Significant relationships/correlations will guide the addition of demographic variables to the analysis.

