Heterogeneity of Treatment Effect - Exploratory use of interaction terms will assess whether significant effects of the study intervention differ by sex or by age (i.e., above vs below 70 years). If found to be present, any such heterogeneity of treatment effect, not having been hypothesized in advance, will be reported as a preliminary finding that awaits confirmation in future studies.

Internal/External Validity and Avoidance of Bias - To limit possible confounding of the primary results, analyses of the prespecified hypotheses will be adjusted for covariates (age, sex, physical fitness at pre-surgical baseline). To assess the representativeness of study participants, their demographic characteristics (sex, age) will be compared to those of eligible patients who are approached for consent but decline to participate in the study. Our digital engagement platform will initiate reminder systems to reduce loss to follow-up.

Statistical Methods by Study Aims - Characteristics considered as potential covariates in all analyses will be age, sex, surgical technique, residential setting, and physical fitness at preoperative baseline. Any covariate that improves the model's fit to the observed data will be retained in the final analysis.

The analyses for Aims 1-3 will be by intention to treat (ITT); the ITT population will include all subjects who have given informed consent, been randomized to intervention or control arm, and undergone the planned cancer surgery.

Aim 1 – Allowing for an anticipated 20% attrition in use of accelerometer by Day 14 across both trial arms, an initial sample size of 332 (randomized 1:1) will provide (per East 6.5 software)

80% power to detect the hypothesized 14% difference in slope due to study intervention, using a 1-sided, repeated measures-difference of slope test with alpha=0.025.

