The Aim's primary endpoint will be the percent change from preoperative baseline in daily step count during the first 2 weeks post-discharge from hospital (measured on Discharge Day, Day +7, and Day +14). percent change from preoperative baseline in daily step count during the first 2 weeks post-discharge from hospital (measured on Discharge Day, Day +7, and Day +14). To recognize that these data may be missing not at random (ie, due to adverse event, distress, or withdrawal of consent), the effect of study intervention on primary endpoint will be modeled jointly with early withdrawal from data collection of that endpoint. Within the joint model, the sub-model for the primary endpoint will use generalized linear mixed modeling (with treatment and covariates as fixed factors, patient ID as random factor), while the other sub-model will analyze time to early withdrawal (Aim 3's primary endpoint) using proportional hazards regression. Similar joint modeling will be carried out for Aim 1's secondary endpoints (change from baseline in sedentary time, general symptoms, disease-specific symptoms).

Aim 2 – Because the CCI is derived from data routinely entered in the medical chart, no loss to follow-up is anticipated for this endpoint. A sample size of 332 subjects randomized 1:1 will provide (per East 6.5 software) 88% power to detect the hypothesized CCI benefit, using a 1-sided test of proportions, unpooled estimate of variance, critical p-value for efficacy=0.024, cumulative alpha=0.025.

The Aim's primary endpoint will be maximum Comprehensive Complications Index (CCI) during the 30 days post-discharge. Maximum CCI will be categorized as above vs below 15, and logistic regression will be used to evaluate the effect of study intervention. The Aim's secondary endpoint, time to hospital readmission through 90 days, will be subjected to survival analysis, handling any early withdrawal from study as a competing endpoint.

Aim 3 - The trial's sample size of n=332 will provide (per SAS software, PROC POWER for two-sample comparison of proportions) at least 80% power.

Treatment will be evaluated for association with this Aim's primary endpoint, time to early withdrawal, using proportional hazards regression. This analysis will be generated as a sub-model of the joint modeling for Aim 1.

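### The primary models' covariates are left to outcome-driven and conflicting rules, and diagnosis, a randomisation stratum, is in none of them

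*Combined protocol and SAP*

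**What the plan says.** Section 13.2 gives three covariate rules and does not say which governs.

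- **Internal/External Validity and Avoidance of Bias:** "analyses of the prespecified hypotheses will be adjusted for covariates (age, sex, physical fitness at pre-surgical baseline"). This reads as mandatory.
- **Statistical Methods by Study Aims:** the "potential covariates in all analyses will be age, sex, surgical technique, residential setting, and physical fitness at preoperative baseline". It continues: "Any covariate that improves the model's fit to the observed data will be retained in the final analysis". This is conditional, and no criterion (AIC, likelihood-ratio test, p-value threshold) or order of selection is given.
- **Preliminary Analysis:** "Prior to hypothesis testing, the relationship between demographic variables and primary outcome variables (daily step count, postop complications) will be examined". Then: "Significant relationships/correlations will guide the addition of demographic variables to the analysis". This screen covers step count and complications, so Aims 1 and 2.

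The model descriptions do not settle the matter. The Aim 1 sub-model is specified "with treatment and covariates as fixed factors, patient ID as random factor", without a list. The Aim 2 logistic regression names no covariates.

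On randomisation, section 4.4 says: "Strata will be defined by diagnosis (GI, GU, GYN) and surgical technique (minimally-invasive versus open"). Technique is only a candidate covariate. Diagnosis appears in none of the three rules.

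Physical fitness is not tied to a measure. The study calendar (section 10.0) lists three preoperative tests at T1: 6MWT, TUG and SPPB.

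**The concern.** A covariate cannot be both certain to enter and kept only if it improves fit. Two statisticians following this plan could fit different primary models and both be compliant, and the choice between the models would be made with outcomes in view. Aims 1 and 2 are powered as one-sided confirmatory tests, so their models should be settled beforehand. In logistic regression the issue goes beyond precision, because the covariate set determines which conditional odds ratio is being estimated.

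The strata raise a second issue. Stratified randomisation balances the arms on diagnosis and technique, which reduces the true variance of the treatment contrast when those factors are prognostic. A model that ignores them still uses the larger variance. The test is then conservative, and the precision gained by stratifying is partly lost.

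**Working it through.** **The plan's own figures.** Aim 2 states 88% power (332 patients 1:1, one-sided, unpooled variance, critical p 0.024). Aim 1 states 80% (one-sided 0.025). Neither can be reproduced, because the Aim 2 event rates and the Aim 1 standard deviation and correlation are not given. For Aim 2, 88% is consistent with assumed control/treated rates such as 30%/15.7% or 40%/24.1%. The stated powers are taken as given below.

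**1. Does fit selection itself inflate error?** Aim 2 logistic simulation at one-sided 0.024, n = 332, six strata, control risk about 33%. AIC is assumed as the criterion because the plan names none. The prognostic case uses assumed log odds ratios: 0.4 per SD for age, -0.4 per SD for fitness, 0.3 for sex and technique, and -0.45/0/+0.45 for diagnosis. There were 15,000 null runs (SE about 0.0012) and 5,000 power runs per case.

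| Case | Error: fixed three | Error: fit-selected | Error: fixed three plus strata | Power, same order |
|---|---|---|---|---|
| Nothing prognostic | 0.0253 | 0.0241 | 0.0257 | 85.0 / 85.3 / 85.0% |
| Prognostic | 0.0205 | 0.0212 | 0.0234 | 86.9 / 86.9 / 87.6% |

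With a real effect, the fixed-three and fit-selected rules reached different verdicts in 1.04% and 0.88% of trials. The 5th to 95th percentile of the ratio of their odds ratios was 0.969–1.033 and 0.980–1.039.

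**2. What if the choice is not tied to one rule?** Five candidates give 2^5 = 32 subsets. A separate simulation at one-sided 0.025 used three assumed covariate strengths (joint R² about 7%, 23% and 55% on the continuous scale). Taking the most favourable of three rules (fixed three, AIC on all five, fixed three plus AIC on the rest) gave error of at most 0.0276 (continuous) and 0.0260 (binary). Taking the best of all 32 subsets gave 0.036 / 0.040 / 0.051 (continuous) and 0.029 / 0.033 / 0.045 (binary). The last is an extreme bound.

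**3. Omitting diagnosis, Aim 2.** The documents give no complication rates by diagnosis. Section 2.1 gives readmission rates, used here only as a proxy: "30- and 90-day readmission rates are 30% and 43% for cystectomy, and 22% and 35% for esophagectomy and pancreatectomy", and a 90-day range across tumour sites of 23% to 43%. For equal-sized groups with mean risk m, R² = variance of group risks / [m(1−m)].

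- 43% v 35%: 0.0016/0.2379 = 0.67%
- 30% v 22%: 0.0016/0.1924 = 0.83%
- 23/33/43% (middle value assumed): 3.0%
- 43% v 23%: 0.0100/0.2211 = 4.5%

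With z = 1.977 for 0.024 and 1.175 for 88% power:

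- unadjusted error = 1 − Φ(1.977/√(1−R²))
- unadjusted power = Φ(1.175/√(1−R²))
- strata-adjusted power = Φ(3.152/√(1−R²) − 1.977)

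| R² | Error | Power unadjusted | Power adjusted | Marginal OR if within-diagnosis OR is 0.50 |
|---|---|---|---|---|
| 0.67% | 0.0236 | 88.1% | 88.2% | 0.502 |
| 0.83% | 0.0235 | 88.1% | 88.3% | 0.502 |
| 3.0% | 0.0223 | 88.4% | 88.9% | 0.509 |
| 4.5% | 0.0215 | 88.5% | 89.4% | 0.514 |

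A logistic simulation of the same cases put the power difference at 0.2 to 1.1 points.

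**4. Omitting the strata, Aim 1.** The sample-size text uses a difference-of-slope test. There, stratum effects on level cancel and the loss is near nil. The analysis text, however, states no treatment-by-time term, so treatment may be tested as a main effect on percent change. The same formulas then apply with z = 1.960 and 0.842, and an assumed share of variance explained by strata:

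| R² (assumed) | Error | Power unadjusted | Power adjusted | Difference |
|---|---|---|---|---|
| 3% | 0.0233 | 80.4% | 81.2% | 0.8 points |
| 10% | 0.0194 | 81.2% | 84.0% | 2.7 points |
| 20% | 0.0142 | 82.7% | 88.0% | 5.3 points |

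A separate check agreed: about 1, 3 and 5 points, with error down to about 0.0135. These are simple linear models. The joint model and the Aim 3 hazards model were not simulated.

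**The case against.** The strongest reply is that little is at stake. The five candidates are named in advance, the Preliminary Analysis screen comes before hypothesis testing, and section 13.1 justifies combining the three cancer sites by their expected similarity in surgical outcomes. Omitting strata adds no false positives. The Aim 2 proxy is readmission after particular procedures, includes no GYN rate and is not CCI above 15, so its figures are only illustrative.

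Much of this stands, and it limits the size of the point. It does not remove the contradiction. Naming candidates does not fix the model, and nothing says that the screen is done blind to arm. Section 13.1's expectation also sits beside section 2.1, where readmission varies by site and procedure.

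Three stronger readings are tempting but not supported.

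- **Fit selection inflates type I error.** Followed consistently, it adds almost none. The 0.03 to 0.05 bound describes a search that the wording fails to exclude, not one that the plan proposes.
- **Omitting the strata takes power below the stated 80% or 88%.** On the linear approximation, unadjusted power does not fall below the stated figure; what is lost is the gain over a strata-adjusted analysis.
- **Patients who consent by telephone, or the control arm, go without fitness tests.** Section 14.7 allows telephone consent but does not say that testing is skipped. Section 5.1 describes the tests within telemonitoring care, but its Study Procedures place objective functional assessment before randomisation, and the study calendar schedules the tests with no arm restriction.

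**Conclusion.** The point holds on the text. Section 13.2 makes age, sex and fitness both mandatory and conditional, leaves the fit criterion unstated, adds a significance screen, and omits diagnosis from every rule although randomisation is stratified by it. The primary models, and the Aim 2 odds ratio being estimated, are therefore not determined until outcomes have been examined.

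The measured consequences are mostly small. For Aim 2, about 0.1 to 1 point of power is forgone on a readmission proxy. For Aim 1, the loss ranges from near nil to about 5 points, depending on which treatment contrast is tested and on assumed stratum strength. The case for acting rests on fixing the confirmatory models in advance at almost no cost, not on a demonstrated error in the trial's operating characteristics.

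**What to change.** - Delete the significance-based sentence under Preliminary Analysis and the fit-based sentence under Statistical Methods by Study Aims.
- Replace both existing covariate lists, including the sentence stating that analyses will be adjusted, with one list for Aims 1 to 3, fixed before outcomes are examined: diagnosis (3 levels) and surgical technique, both as randomised; age; sex; and one named preoperative fitness measure already scheduled at T1.
- State whether residential setting is in or out, and that no covariate is added or removed using outcome data.
- For a missing fitness value, impute the mean over both arms together, so that no patient in the plan's ITT population (consented, randomised and operated on) is dropped.
- Label any fit-selected model a sensitivity analysis.

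The cost is SAP wording and about 3 more degrees of freedom than the three-covariate set (2 for diagnosis, 1 for technique) in 332 patients. The variables are already planned for collection.

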The proposed **comparators** include the following: Remote Perioperative Telemonitoring Care⁷⁻¹⁵, which will include: 1) objective assessment of functional activity using Actigraph GT9X Link accelerometer with comprehensive assessment of functional capacity to guide prehabilitation needs; 2) subjective ePROs (TapCloud™ digital engagement platform); 3) real-time, RN-driven alert/feedback system based on pre-determined outcome thresholds (daily steps of ≤ 1500 ; 1+ symptoms rated moderate to severe intensity) and triggered based on patient input; and 4) standard post-surgical care. When thresholds are met, RNs will proactively initiate patient contact via TapCloud™ secure messaging followed by telephone calls to assess, triage, and manage. Telemonitoring begins before surgery, and continues after discharge. Surgeon Only Perioperative Care involves routine care by the surgeon/surgical team of functional declines/symptoms. Patients/families will meet with the surgeon at least once before surgery, have pre-anesthesia assessment for pre-op final evaluation, be managed daily during postop inpatient acute care, have first postop visit 1-4 weeks after discharge, with follow-up as needed thereafter. Patient contacts after discharge are primarily reactive through standard procedures,

including: 1) contacting the surgeon if symptoms become severe and physical function worsens; and 2) use of the hospital call line to report problems.

Remote Perioperative Design and Content - The telemonitoring care includes three key components. The first component involves objective assessment of functional activity. Before surgery, we will complete comprehensive functional activity assessment, using three objective functional measures (6 Minute Walking Test, Timed Up and Go, and the Short Physical Performance Battery). These measures, collectively, assesses functional impairments, risk for falls, and lower extremity capacity. Participant's home environment (number of stairs) will also be assessed. Participants will undergo personalized prehabilitation based on assessment findings. We have experience with perioperative physical interventions that begins before surgery.⁷⁰

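### Aim 1's stated 80% power is for a difference-of-slopes test, but the written endpoint and model compare levels, so the figure does not apply to the planned analysis.

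*Combined protocol and SAP*

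**What the plan says.** In the combined protocol and SAP, Section 13.2 (Aim 1) claims 80% power for the "hypothesized 14% difference in slope due to study intervention", "using a 1-sided, repeated measures-difference of slope test with alpha=0.025". The sample is given as follows: "an initial sample size of 332 (randomized 1:1) will provide" this power, "Allowing for an anticipated 20% attrition in use of accelerometer by Day 14 across both trial arms". No SD, within-patient correlation, time axis or unit for the slope is stated.

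The next paragraph of Section 13.2 defines the endpoint as percent change in daily step count from preoperative baseline over the two weeks after discharge, "measured on Discharge Day, Day +7, and Day +14". The sub-model for this endpoint is a generalized linear mixed model with treatment and covariates as fixed factors and patient as a random factor. Neither that description nor the list of candidate covariates names time or a treatment-by-time interaction. The synopsis repeats the same model.

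On timing, Section 5.1 states: "Telemonitoring begins before surgery, and continues after discharge". It also says of the telemonitoring arm: "Participants will undergo personalized prehabilitation based on assessment findings". In the surgeon-only arm, Section 5.1 leaves prehabilitation to the surgical team's discretion and says that it is not standard at these sites.

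**The concern.** A difference in slopes and a difference in levels are separate quantities with separate standard errors. The power statement describes the first, and the endpoint and model describe the second. A reader who takes 80% as the chance that the planned Aim 1 analysis succeeds has no basis for that figure.

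The obvious way to reconcile the two is to add time terms so that the model delivers the slope contrast. That creates another problem. Discharge Day comes after randomization and after the preoperative part of the intervention, so the level on that day is already an outcome. A slope starting there removes whatever the intervention has achieved by discharge.

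**Working it through.** **Inputs from Section 13.2:** 80% power, 1-sided alpha 0.025, a 14% difference in slope, and visits at Discharge Day, Day 7 and Day 14.

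**Assumptions (not in the documents):** 14% means 14 percentage points over the two weeks; the slope starts at Discharge Day, the first listed visit; residual variance is equal across visits with a common within-patient correlation ρ (compound symmetry); normal approximation; attrition is a simple loss of patients.

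**1. The plan's own figure.** The 80% cannot be reproduced forward, because no SD is given. It can only be inverted. With three equally spaced visits, the least-squares slope is (Day 14 − Discharge Day)/14 days, so the test compares the two-week change between arms:

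SE(slope contrast) = 14/(1.960 + 0.842) = 5.00 points.

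This corresponds to an SD of the two-week change of 45.5 points with 166 per arm, or 40.7 points with 133 per arm (332 × 0.8 / 2). The steps below use only the SE, so they do not depend on which of these applies.

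**2. Standard errors of the level contrasts.** Relative to the variance at one visit, the two-week change has variance 2(1 − ρ), the three-visit mean (1 + 2ρ)/3, and the Day 7/14 mean (1 + ρ)/2. Hence:

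- SE(three-visit mean) = 5.00 × √[((1 + 2ρ)/3) / (2(1 − ρ))] = 3.08, 4.08, 5.77 at ρ = 0.3, 0.5, 0.7
- SE(Day 7/14 mean) = 5.00 × √[((1 + ρ)/2) / (2(1 − ρ))] = 3.41, 4.33, 5.95

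**3. Power of the written main effect.** With complete data, a treatment effect without time terms is the arm difference in the mean of the three visits. If the benefit builds linearly (0, 7, 14 points), that mean is 7. Power = Φ(7/SE − 1.960):

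- ρ = 0.3: 7/3.08 = 2.27, power 62%
- ρ = 0.5: 7/4.08 = 1.72, power 40%
- ρ = 0.7: 7/5.77 = 1.21, power 23%

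The size of the effect cancels: replacing 14 by any other two-week difference rescales the effect and the back-solved SE together. The percentages therefore rest on the linear build-up from zero, on ρ and on the 80% being right for the slope, rather than on the unit.

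**4. The slope test when some benefit is present at discharge.** Let a fraction f of a 14-point Day 14 benefit exist at discharge. The slope contrast is then 14(1 − f), with power Φ(14(1 − f)/5.00 − 1.960):

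- f = 0: 80%
- f = 0.25: 10.5/5.00 = 2.10, power 56%
- f = 0.5: 7/5.00 = 1.40, power 29%
- f = 1: contrast 0, power 2.5%, equal to alpha

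Subtracting the same preoperative baseline from every visit does not alter this, because it cancels from the slope.

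**5. Contrasts side by side** (power at ρ = 0.3 / 0.5 / 0.7):

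| Benefit at Discharge, Day 7, Day 14 | Slope | Three-visit mean | Day 7/14 mean |
|---|---|---|---|
| 0, 7, 14 | 80% | 62 / 40 / 23% | 87 / 68 / 42% |
| 7, 10.5, 14 | 29% | 93 / 73 / 44% | 95 / 81 / 54% |

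The Day 7/14 column uses mean effects of 10.5 and 12.25 points. The two level contrasts are not interchangeable, and neither always beats the slope.

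**The case against.** A reader might infer more: that the trial, by testing a slope from discharge, would miss or even reverse a real benefit. The documents do not support that. The model in Section 13.2 has no time terms, so its treatment effect would keep a benefit present at discharge. The test is 1-sided and could not declare surgeon-only care better. A benefit that is large at discharge and gone by Day 14 has no support in the documents. Section 2.4 reports a median of 483 steps in hospital against 6,562 before surgery, about 7% (483/6,562), so gains on Discharge Day may be small, though in-hospital steps are only a proxy. The slope's origin at Discharge Day is also inferred from the listed visits.

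It can be said, too, that the list of fixed factors is shorthand, since Section 13.1 speaks of testing outcomes over time, and that rate of recovery is a defensible target. Both are fair, and if benefit builds only after discharge, the slope can be the more powerful contrast. But testing over time does not specify a slope, and if a slope is meant, step 4 of the working applies. Under either reading the plan has to say which contrast is primary and power that one.

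**Conclusion.** The point stands as a mismatch between the power statement and the planned analysis. The 80% refers to a slope contrast that is neither the written endpoint nor the effect estimated by the written model, and no power is stated for the contrast that the model does estimate. For a benefit growing linearly from zero at discharge, that power is about 62%, 40% or 23% at ρ = 0.3, 0.5 or 0.7; it is higher if some benefit is already present at discharge.

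These are conditional figures. They rest on a back-solved SE, compound symmetry and an assumed range for ρ, and they leave out the joint model with withdrawal. Covariate adjustment would lower the correlation that matters, so ρ should be read as the value after adjustment. The cancellation of a maintained discharge benefit in a slope needs none of these assumptions, but how much it would cost is unknown, because the documents give no estimate of the benefit at discharge.

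**What to change.** 1. Prespecify one level contrast as the Aim 1 primary estimand: for example, the arm difference in percent change from preoperative baseline averaged over Days 7 and 14.
2. Estimate it from a mixed sub-model with arm, visit and arm-by-visit terms, kept within the joint model with early withdrawal.
3. Re-run the power for that contrast and state the SD, the correlation, the unit of the effect and the assumed benefit at each visit. Replace the slope-based sentence in Section 13.2.
4. Report the slope from discharge as supportive.

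The cost is SAP wording, matching text in the synopsis and one new power run; no new data are needed. The stated 80% will change and may fall. A level contrast can also be less powerful than a slope if benefit builds only after discharge: in the 0, 7, 14 case the Day 7/14 mean gains at ρ = 0.3 (87%) but loses at 0.5 and 0.7 (68% and 42%, against 80% for the slope).

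### Aim 1's percent-change analysis does not secure adjustment for preoperative step count, so a modest amount of precision is given up for no benefit

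*Combined protocol and SAP*

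**What the plan says.** Section 13.2, Aim 1, sets the primary endpoint as "percent change from preoperative baseline in daily step count during the first 2 weeks post-discharge from hospital", taken at discharge and at days 7 and 14. The outcome sub-model is "generalized linear mixed modeling (with treatment and covariates as fixed factors, patient ID as random factor"), fitted jointly with time to early withdrawal. No transformation, distribution or link is given.

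Two statements in the same section deal with covariates. The paragraph on validity and bias says "analyses of the prespecified hypotheses will be adjusted for covariates (age, sex, physical fitness at pre-surgical baseline"). The opening of the methods by aim lists the candidates as "age, sex, surgical technique, residential setting, and physical fitness at preoperative baseline" and adds: "Any covariate that improves the model's fit to the observed data will be retained in the final analysis". Neither names preoperative step count. Physical fitness is not defined. The preoperative functional tests in Section 12.1.3 and Table 4 are the six-minute walk, the timed up-and-go and the SPPB, which is the more natural meaning.

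Power is stated as "80% power to detect the hypothesized 14% difference in slope due to study intervention", "using a 1-sided, repeated measures-difference of slope test with alpha=0.025", with "an initial sample size of 332 (randomized 1:1") and 20% loss of accelerometer data by day 14.

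**The concern.** Dividing by baseline does not remove its influence. Unless post-discharge steps rise in strict proportion to preoperative steps, patients with low baselines tend to show higher percent-change values and patients with high baselines lower ones. That relationship is predictable, and without a baseline term it stays in the residual variance. If one arm happens to have lower preoperative steps, nothing in the analysis corrects for it. Section 4.4 stratifies on diagnosis and surgical technique only, so the design does not balance baseline steps either.

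What is at stake is precision in a primary comparison planned at 80% power, and whether the adjustment is fixed in advance or depends on a fit rule applied to the trial's own data.

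**Working it through.** **The plan's own figure.** For a two-group comparison, power = Φ(δ/(SD·√(2/n)) − 1.96), and 80% power needs δ/SE = 1.960 + 0.842 = 2.802. The documents give δ = 14 but no SD, so the 80% can only be back-solved: SD = 14/(2.802·√(2/n)).
- With n = 166 per arm, SD = 45.5 percentage points.
- With n = 132.8 per arm (166 × 0.8), SD = 40.7.

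At 132.8 per arm, power would be 90% if the SD were 35, 81% at 40, 63% at 50 and 48% at 60. The stated 80% is neither confirmed nor refuted.

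**Average effect, closed form.** Assume log-normal steps with log-SD s0 before surgery and s1 after, and correlation ρ between them. Let τ² = s0² + s1² − 2ρ·s0·s1. Percent change is a linear function of the ratio of post to baseline steps, so its correlation with log baseline is r = (ρ·s1 − s0)/√(exp(τ²) − 1). Adjustment multiplies the residual variance by 1 − r², so δ/SE rises from 2.802 to 2.802/√(1 − r²). The s0, s1 and ρ values are assumptions.

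| s0 / s1 / ρ | ρ·s1 − s0 | τ² | r | 1 − r² | δ/SE | Power (from 80%) |
|---|---|---|---|---|---|---|
| 0.5 / 0.7 / 0.7 | −0.01 | 0.250 | −0.02 | 1.000 | 2.80 | 80% |
| 0.6 / 0.7 / 0.6 | −0.18 | 0.346 | −0.28 | 0.922 | 2.92 | 83% |
| 0.8 / 0.9 / 0.3 | −0.53 | 1.018 | −0.40 | 0.841 | 3.06 | 86% |

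The same r gives the effect of chance imbalance. If mean log baseline differs between arms by one standard error, the unadjusted estimate moves by |r| of its own standard error, which is about 0.3 to 0.4 in the last two rows.

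**Average effect, simulation.** There were 166 patients per arm, with 10% dropout before day 7 and 20% by day 14. Pilot medians came from Section 2.4: 6,562 before surgery, 1,689 at day 7, and 2,483 (the two-week figure) used for day 14. The following were assumed: discharge median 1,000, log-SD 0.4–0.8 before and 0.5–0.9 after, correlation 0.3–0.8, and within-patient log-SD 0.3–0.5. The effect was set so that unadjusted percent change had about 80% power. With an effect constant over visits, adding log baseline gained about 1 to 7 points. For a multiplicative effect, examples are 78.9% to 84.3% (0.8/0.9/0.3), 77.3% to 80.0% (0.8/0.9/0.6) and 78.1% to 79.0% (0.6/0.6/0.8). A simpler design with one post-discharge value per patient gave about 0 to 10 points under log-normal and gamma steps, with no material loss.

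**Difference of slopes, simulation.** In the same set-up, with the effect multiplicative and growing over time, adding baseline moved power as follows:
- 0.6/0.7/0.6: 79.1% to 80.5%
- 0.8/0.9/0.3: 80.1% to 82.9%
- 0.8/0.9/0.6: 79.3% to 79.8%
- 0.6/0.6/0.8: 76.9% to 77.4%

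The gain is about 0.5 to 3 points. Here each patient's slope was regressed on baseline, which in a mixed model corresponds to a baseline-by-time term. A main effect of baseline alone would add almost nothing to a slope contrast.

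Per-patient means and slopes stood in for the mixed model, and the joint withdrawal sub-model was not simulated.

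**The case against.** The strongest defence has three parts. First, physical fitness is undefined and might be meant to include steps, and one sentence promises adjustment for it. That weakens any claim that the plan excludes baseline steps, but it does not secure them: the term more naturally means the functional tests, and the retention rule could still drop it. Second, the test that was powered compares slopes, where baseline adds at most a few points. That stands and limits the size of the point. Third, the minimum wear-time rule in Section 12.1.3 would reduce baseline noise if baseline averages several valid days. This is fair, but the plan does not state it, and averaging does not remove the correlation between percent change and baseline.

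A reader might infer two stronger conclusions. One is that the comparison is biased. It is not: allocation is randomised, and a null simulation of the unadjusted test rejected 2.6% of the time against a nominal 2.5%. Only the conditional effect of a chance imbalance remains.

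The other is that a log-step model should replace percent change because it recovers substantial power. With log-normal steps and a constant multiplicative effect, simulated power did rise from 77–83% to 83–99%. That depends on the assumed distribution, and the documents give medians only. In the single-value design (133 per arm, baseline log-SD 0.5, correlation 0.5), gamma steps reversed the gain: 84% against 82% at shape 2, and 91% against 82% at shape 1.2. With an assumed 5% of zero counts, percent change had about 77% power and the log model 20%, 53% or 72% for offsets of 1, 100 or 1,000. For the slope test, the log scale changed power by −5 to +19 points. It also changes the estimand: a constant multiplicative effect appears as a slope difference on the percent scale (31–47% power) but not on the log scale (about 2.5%).

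**Conclusion.** The point holds as a matter of precision and prespecification. The plan analyses percent change without guaranteeing adjustment for preoperative steps. The expected gain from fixing this is modest: roughly 0 to 10 power points for an average treatment effect and about 0.5 to 3 points for the difference of slopes. Both ranges rest on assumed SDs and correlations, and the gain is nil where ρ·s1 is close to s0. The validity of the randomised comparison is not in question, and the documents do not support replacing the endpoint's scale. The change is worth making because it uses data already in hand and showed no material loss in the scenarios examined.

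**What to change.** Keep percent change as the Aim 1 endpoint. In Section 13.2 and the matching synopsis text, name log preoperative daily steps as a prespecified fixed covariate in the mixed model, retained regardless of fit, and exempt it from the covariate-retention rule. Define the baseline window and take it from days before allocation; Sections 4.3 and 5.1 should agree on that order. If the primary contrast is the difference of slopes, include the baseline-by-time term as well, because the small gain for slopes comes from it. State the SD and correlation behind the 80% power.

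A log-step model with log baseline, reported as a ratio with a 95% confidence interval, can be added as a sensitivity analysis with a stated rule for zero-step days.

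The cost is SAP wording and one or two model parameters. Table 4 already schedules steps before surgery. A patient without a usable baseline has no percent change either, so the covariate excludes no one further. The hypothesised 14% and the sample size need not change.
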